8. FOR FIRST COHORT ONLY, NOT REQUIRED FOR BIOMARKER COHORT: Patients will be allowed to eat pomegranates and drink pomegranate juice provided that the patient has been taking these for 4 weeks or more with evidence of progressive disease as outlined above (Inclusion Criteria 3.0). These patients should be instructed to continue to take pomegranates and/or pomegranate juice as per the same schedule while on study. Documentation of amount and duration will be captured for those patients taking pomegranates or pomegranate juice. Those patients who have not been taking pomegranates or pomegranate juice prior to study entry will not be allowed to begin these while on study.
9. Patients must not have evidence of bone metastases or lymph node involvement as determined by bone scan or CT scan of the abdomen and pelvis within 4 weeks of study registration. Note: NaF-PET/CT scan information will NOT be used to determine evidence of metastases for eligibility purposes or for defining disease progression.

10. Patients must not have been treated with a prior vaccine therapy for prostate cancer.
11. Patients must not have known psychological or sociological conditions, addictive disorders or family problems, which would preclude compliance with the protocol.
12. Patients must not have known allergic reactions to GM-CSF.
13. Patients with unstable or severe intercurrent medical conditions or laboratory abnormalities that would impart, in the judgment of the Medical Monitor, excess risk associated with study participation or study agent administration.
14. Patients cannot have concurrent enrollment on other phase I, II, or III investigational treatment studies.

8. Experimental Design

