nomogram(<http://www.mskcc.org/applications/nomograms/prostate/PsaDoublingTime.aspx>). The post-treatment PSA doubling time will be calculated using the same nomogram from:

- (1) All PSA values obtained from the same clinical laboratory using the same PSA assay beginning with the PSA value at day 1 (week 0) and continuing until the end-of study (or month 24) value (PSADT₀₋₂₄).

(2) All PSA values obtained from the same clinical laboratory using the same PSA assay beginning with the PSA value at day 85 (month 3) to the day 253 (month 9) value (PSADT₃₋₉).

An increase in the PSA doubling time to at least double the baseline value, and at least 15 months, will be considered a PSA doubling time “response” [7].

D. Quantitative Total Bone Imaging (QTBI) using NaF PET/CT

An assessment of small volume bone metastatic disease (potentially not detected by standard bone scintigraphy) and tumor growth rates will be conducted using QTBI. Patients accrued to the Biomarker Cohort at designated clinical trial sites will be assessed at baseline, 3 months and 6 months by NaF PET/CT. Metastatic prostate cancer lesions in bone will first be localized and identified based on functional NaF PET uptake, assisted with the anatomical information provided by CT scans. Segmentation will be performed using an automatic segmentation method (e.g. a fixed SUV threshold), and adjusted with physician guidance. Scans from different time points will be registered to one another using an articulated registration technique employing a rigid registration of skeletal elements (bones) from CT followed by registration optimization by combining with deformable registration of bones and lesions from NaF PET/CT. The lesions between pre-treatment and follow-up scans will be matched to establish longitudinal correspondence of the lesions. For each patient, comprehensive treatment response metrics will be calculated, consisting of SUV_{total} (total disease burden), SUV_{max} (maximum intensity lesion), SUV_{mean} (average intensity), the number of lesions, and total volume of bone lesions. In addition, imaging response metrics will be calculated for each individual lesion. This methodology will specifically be used to assess the growth rate of bone metastatic disease by evaluating changes from baseline to month 3 and from month 3 to month 6. In terms of logistics, each of the clinical centers has the capacity and expertise to perform NaF PET imaging.

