- 1) Baseline immune responses specific for PAP (by antigen-specific T cell proliferation, cytokine release or regulatory response by tvDTH) will be evaluated in all subjects, blinded to treatment arm.
- 2) Sera obtained at baseline and at 6 months will be used to identify whether antibody responses are elicited to other prostate-associated antigens.
- 3) Quantitative Total Bone Imaging (QTBI) will be evaluated in a blinded fashion at baseline, 3 months and 6 months. QTBI parameters will include: Standardized Uptake Values (SUV): SUVmax, SUVtotal, SUVmean, SUVpeak and volume. These image data will be used:
 1. To determine whether the presence of lesions detected by NaF PET/CT at baseline is associated with early disease progression (within 1 year) by standard radiographic imaging methods (CT and bone scintigraphy)
 2. To determine whether NaF18F- PET/CT reveals different patterns of disease progression with respect to treatment arm.
 3. To determine if growth rates, and changes in growth rates, determined by NaF PET/CT are associated with PSA doubling time and changes in PSA doubling time (PSADT₀₋₂₄, PSADT₃₋₉).

Statistical Analysis Plan

Analysis populations:

Intent-to-Treat (ITT) Population: The primary population for the efficacy analysis will be the ITT population, defined as all patients who have been randomized and have received at least one dose of pTVG-HP/rhGM-CSF or rhGM-CSF treatment.

Evaluable Efficacy Population: The secondary population for the efficacy analysis will be the Evaluable Efficacy Population. The Evaluable Efficacy Population consists of all patients who have been treated according to protocol, i.e., all inclusion/exclusion criteria are satisfied, adequate compliance with treatment (having received all pTVG-HP/rhGM-CSF or rhGM-CSF treatment until a study endpoint was reached), and have completed all radiographic assessment (until a study endpoint was reached).

Safety Population: The Safety Population for assessment of safety consists of all patients who received at least one dose of pTVG-HP/rhGM-CSF or rhGM-CSF treatment.

Primary endpoint:

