The detection of antigen spread to other prostate associated antigens, and the identification of specific antigens recognized, will be analyzed descriptively. In addition, logistic regression analysis will be conducted to evaluate whether antigen spread is associated with the generation of PAP-specific immune responses elicited as a result of treatment. The dependent variables will be the detection of IgG responses to ≥ 1 “off-target” antigen at 6 months (and not present pre-treatment) while treatment arm and 6-month PAP-specific immune responses (no vs. yes) will be included as covariates. The results will be reported in terms of odds ratios and the corresponding 95% confidence intervals.

Results from the QTBI analysis will be used to determine whether individuals with identifiable bone lesions exhibit early disease progression (within 1 year) by standard bone scintigraphy and/or CT scans, and whether the time to metastatic disease is different with respect to treatment group. Specifically, the association between baseline QTBI parameters and time to disease progression will be evaluated using Cox proportional hazard analysis. Analogously, logistic regression analysis will be conducted to evaluate presence of lesions detected by NaF PET/CT at baseline is associated with early disease progression (within 1 year) rate.

Furthermore, % changes in QTBI parameters from the baseline to the 3 and 6 months assessment will be calculated and summarized in terms of means, standard deviations, medians and ranges, stratified by treatment arm. A linear mixed effects model with subject specific a random effects will be used to evaluate the association between changes in QTBI parameters and changes in PSA doubling time.

Due to the exploratory nature of the biomarker evaluations proposed in this trial, no adjustments will be made for multiple comparisons. Except for the primary endpoint which will be compared

at the one-sided 5% significance level, all other comparisons will be made using a two-sided test at a significance level 0.05 without adjustment for multiplicity. Data analysis will be conducted using SAS software (SAS Institute, Carey NC), version 9.3 or greater.

14. Administrative Considerations

A. Specimen Handling

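### The by-arm QTBI summary uses percent change from baseline, which has no value for men without a NaF lesion at baseline, including those who then develop lesions

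*Combined protocol and SAP*

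**What the plan says.** Section 13, Statistical Analysis Plan, Biomarker endpoints: percent "changes in QTBI parameters from the baseline to the 3 and 6 months assessment will be calculated and summarized" as means, standard deviations, medians and ranges, by treatment arm. The next sentence plans a linear mixed effects model to "evaluate the association between changes in QTBI parameters and changes in PSA doubling time"; it does not say whether change is percent, absolute or logarithmic.

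Section 13, Study Endpoints, lists the QTBI parameters as "SUVmax, SUVtotal, SUVmean, SUVpeak and volume". Section 11.D describes how they arise: "Metastatic prostate cancer lesions in bone will first be localized and identified based on functional NaF PET uptake", after which lesions are segmented and the metrics calculated. That section adds "the number of lesions, and total volume of bone lesions" and describes growth rate as "evaluating changes from baseline to month 3 and from month 3 to month 6", again without a scale.

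On who is scanned, Section 7.B item 9 states: "Patients must not have evidence of bone metastases or lymph node involvement as determined by bone scan or CT scan". The same item adds that "NaF-PET/CT scan information will NOT be used to determine evidence of metastases for eligibility purposes". The biomarker cohort has 50 men, 25 per arm (Section 13, Power Calculation), and NaF scans are done at two sites only (study calendar footnote; Sections 10.B, 10.F and 10.H).

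**The concern.** Percent change needs a non-zero baseline. This cohort is selected to have no bone metastases on conventional imaging, so some men can be expected to have no lesion on the baseline NaF scan either. For them the planned measure does not exist, and the protocol and SAP give no rule for a zero baseline, for a lesion-based metric when there is no lesion, or for new lesions.

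The values lost include the most informative ones. A man who goes from no lesion to several shows clear growth in bone, yet he contributes nothing to the table. Section 2.D wants to know whether treatment affects tumour growth in bone and whether the pattern of progression differs by arm. A by-arm table limited to men already positive at baseline speaks to that only in part.

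**Working it through.** The plan states no figure on this point, so there is none to reproduce. The check is of the definition, followed by a range for the number of men affected.

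**1. Are zero baselines expected?** Section 7.B requires negative conventional imaging and ignores the NaF result, so men with and without NaF lesions can both enter. Section 13 plans a logistic regression of progression within 1 year on whether a NaF lesion is present at baseline. That analysis needs men in both groups.

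**2. What are the metrics with no lesion?** Section 11.D computes them from identified lesions. On that reading SUVtotal, volume and lesion count are 0. SUVmax, SUVmean and SUVpeak have no lesion to be measured on. None of the five parameters listed in Section 13 then has a usable baseline for a percent change. Lesion count is not in the Section 13 list, so it is affected only if it is summarised.

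**3. The formula.** Percent change = 100 × (follow-up − baseline) / baseline. Illustrative burdens in arbitrary units:

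| Baseline | Follow-up | Percent change | Absolute change | Change in log(1 + x) |
|---|---|---|---|---|
| 0 | 0 | 0/0, undefined | 0 | 0 |
| 0 | 5 | 5/0, undefined | +5 | ln 6 − ln 1 = 1.79 |
| 0.5 | 5 | 100 × 4.5/0.5 = +900% | +4.5 | ln 6 − ln 1.5 = 1.39 |
| 5 | 10 | 100 × 5/5 = +100% | +5 | ln 11 − ln 6 = 0.61 |

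The absolute and log versions give every man a value. The third row shows a lesser problem: a small non-zero baseline gives a very large percentage, which distorts the planned means and standard deviations.

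**4. How many men?** Let N be the number scanned and p the share with a baseline NaF lesion. The number with no defined value is N × (1 − p). The documents give no p, and N may be below 50 because only two sites scan. Both are therefore varied; N = 30 is an assumption.

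| p (assumed) | No value, N = 50 | No value, N = 30 |
|---|---|---|
| 10% | 45 | 27 |
| 25% | 37.5 | 22.5 |
| 50% | 25 | 15 |
| 75% | 12.5 | 7.5 |
| 90% | 5 | 3 |

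If 30% to 70% have no baseline lesion and all 50 are scanned, the loss is 50 × 0.30 = 15 to 50 × 0.70 = 35 men. At p = 25%, 50 × 0.25 / 2 = 6.25, so about 6 men per arm would have a value.

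**The case against.** Percent change is written only for the descriptive summary. A reader might infer that men without a baseline lesion also drop out of the mixed model, so that exploratory objective 5 is answered in a selected subset. The documents do not support that: the model sentence and the growth-rate text in Section 11.D say only that changes are used. This stands. What remains for the model is an unstated scale.

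A reader might also infer that the trial discards new bone disease. It does not. Section 11.D computes lesion counts and per-lesion metrics matched across scans, and its month 3 to month 6 interval gives a non-zero start to a man whose first lesion appears at month 3. Section 13 lists patterns of progression by arm as a separate use of the images. Metastases for the primary endpoint come from conventional imaging. The omission is from the planned by-arm summary.

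Nor does a negative bone scan imply a negative NaF scan. Section 2.D suggests that NaF PET/CT may be the more sensitive method, so the share affected could be small. That is why the size is given as a range.

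Section 2.D draws an analogy with PSA doubling time, which is a reason to keep a relative scale. It supports percent change as a supplement but does not make it defined at zero.

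Finally, Section 11.D refers image analysis to a separate operating procedure that may say how lesion-free scans are scored. It is not part of these documents, and the statistical section does not cite it for this purpose.

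**Conclusion.** The point holds for the by-arm descriptive summary: as specified, it has no value for any man without a baseline NaF lesion, whether he stays clear or develops lesions. This follows from the plan's own definitions, assuming that the metrics are computed on identified lesions only, as Section 11.D describes.

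The size is unknown. The 15 to 35 men out of at most 50 restates an assumed 30% to 70% without a baseline lesion; it is not an estimate. For the mixed model and objective 5, the same loss is possible and not shown. The analysis is exploratory and the primary analysis is unaffected, so this is a worthwhile improvement of low severity.

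**What to change.** In Section 13, Biomarker endpoints:

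- Summarise by arm, for all scanned men, the absolute change (or the change in log(x + constant), with the constant fixed in advance) in SUVtotal, lesion volume and lesion count. Count new lesions from zero. Use medians and rank-based summaries, because the values will be skewed.
- Keep percent change as a supplementary description in men with a baseline lesion, and report how many they are in each arm.
- State that the mixed model uses a scale defined at zero, and name it.
- State a no-lesion convention for SUVmax, SUVmean and SUVpeak. Absolute change does not solve the problem for these three. One option is to report them only where a lesion exists at both scans, with the number of such men shown.

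The cost is SAP wording only, since the planned scans already supply the data. The drawbacks are skewed values and, for the log version, results that depend on the chosen constant. Settling this before unblinding avoids a choice made after seeing the results.

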APPENDIX A

NCI Common Terminology Criteria – Version 4

http://ctep.cancer.gov/protocoldevelopment/electronic_applications/docs/ctcaev4.pdf

APPENDIX B

Blood Draws for Research

	Screen ¹	Month 3	Month 6	Month 9	Month 12	End of Study
Sera for Antibody	20mL	10mL	10mL	10mL	10mL	10mL
Blood for T-cell response	Leukapheresis Or ² 200mL	100mL	Leukapheresis Or ² 200mL	100mL	100mL	100mL
Approximate Total	20mL (+Leuk.) Or 220mL (-Leuk.)	110mL	10mL (+Leuk.) Or 210mL (-Leuk.)	110mL	110mL	110mL

¹Blood and leukapheresis samples at screening must be collected before tetanus immunization.

²200mL peripheral blood draw is an alternative if leukapheresis is not feasible.

Volumes in the table are approximate and are to be used for determining how many and which tubes are to be drawn per the protocol. Blood sera for antibody testing is to be collected in red top tubes and blood for T-Cell response is to be collected in green top heparinized tubes (or via leukapheresis at Screening and Month 6).
